IV dosing with otilimab or placebo		X						Approximately 1-hour IV infusion. Record start and end times of the infusion. Randomization and Dosing should be as close as possible on the same day.

1. Assessment to be conducted on Days 4 and 7 (if not discharged).
2. Assessment to be conducted every day from Day 1 until Discharge (or until Day 28 if the participant remains hospitalized).
3. Up to 48 h before randomization. If Screening and Randomization are within 24h, there is no need to repeat Day 1 pre-dose assessments (except Ordinal Scale and pre-infusion vital signs).
4. Consent may be collected before the 48h screening window if the investigator considers that the participant is likely to become eligible, and wants to ensure that consent is given by the participant (rather than an LAR).
5. If the participant is discharged before Day 13, the Day 14 and Day 28 visits will be replaced with a phone call (± 2 days). If the participant is discharged on Day 13, the Day 14 visit is not required, and the Day 28 visit will be a phone call (± 2 days). When visits are replaced with a phone call, complete the same assessments as the Day 42 or 60 phone call.
6. If the participant is discharged between Day 15 and Day 27, the Day 28 visit will be replaced with a phone call (± 2 days). When visits are replaced with a phone call, complete the same assessments as the Day 42 or Day 60 phone call.
7. Follow-up phone calls at Day 42 (± 2 days) and Day 60 (± 2 days). If the participant has not been discharged, these will be visits.
8. See Section 6.7 for information on Early Withdrawal.
9. At Screening, record COVID-19 current vaccination status, and any other prior medications within 14 days before Screening.
10. If a cytokine release syndrome (CRS) related to drug is suspected (see Section 7.4.7.1), the following samples should be taken as soon as possible after suspected CRS onset and again 24 h later: Hematology, CRP, D-dimer, ferritin, PD sample (cytokines).
11. Sample can be collected anytime from Screening up to start of infusion.
12. Days 2, 4 and 7 only.
13. Immediately after infusion.
14. Days 2 and 7 only.
15. If central laboratory kits for PK/PD sampling are not available at a site (for operational reasons), participants can be randomised and dosed, and the PK or PD samples not collected (refer to Section 7.5 and Section 7.7).

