6.8. Lost to Follow Up

A participant will be considered lost to follow-up if he or she is unable to be contacted by the study site after discharge from hospital. Every effort must be made to reduce missing data.

- The site must attempt to contact the participant as soon as possible and counsel the participant on the importance of maintaining the assigned study schedule and ascertain whether or not the participant wishes to and/or should continue in the study.
- Before a participant is deemed lost to follow up, the investigator or designee must make every effort to regain contact with the participant (where possible, 3 telephone calls and, if necessary, a certified letter to the participant's last known mailing address or local equivalent methods). These contact attempts should be documented in the participant's medical record.
- Should the participant continue to be unreachable, he/she will be considered to have withdrawn from the study.

Discontinuation of specific sites or of the study as a whole is described in Section 9.1.9.

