8.4.2. Primary Endpoint(s)

The primary endpoint is whether or not a participant is alive and free of respiratory failure at Day 28.

The primary endpoint was analysed when all participants in Part 1 had completed Day 28. In Part 2, the primary endpoint will be analysed after all participants have completed Day 28. The final analysis will be conducted for each part of the study after the last participant has completed the study. Participants are considered alive and free of respiratory failure if they are in category 1, 2, 3 or 4 from the GlaxoSmithKline (GSK) modified version ordinal scale adapted from World Health Organization (WHO) scale 2020 (Section 7.2.6. Table 2 - Ordinal Scale).

Part 1 and Part 2

The primary estimand is the odds ratio between otilimab versus placebo in the proportion of participants alive and free of respiratory failure at Day 28 in participants with severe pulmonary COVID-19 related disease regardless of use of additional medications or changes to standard of care. No other intercurrent events are expected and the strategy for analysis will be to use the treatment policy strategy, with data analyzed as collected. It is expected missing data will be minimal and most will be lost to follow up data after discharge and this along with intermittent data will be imputed using multiple imputation under the missing at random assumption. Every effort will be made to reduce missing data. Supplemental estimand strategies and missing data sensitivities may be performed and further details will be provided in the analysis plan.

The primary endpoint will be summarized using counts and proportions of the number of participants alive and free of respiratory failure and will be analyzed using a logistic regression model, adjusting for ordinal scale category at baseline and age group. The outcome of the model is an odds ratio, and a confidence interval for the odds of improvement in proportion of participants alive and free of respiratory failure at Day 28.

In addition, the corresponding difference in proportion and confidence interval will be calculated from the model [Ge, 2011].

The analysis of the primary endpoint at the in-stream interim analyses in Part 1 will be the same as that described for the primary endpoint above.

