4.3.2.2. Time to Event Endpoints

The following endpoints will be analysed using time to event analyses with a follow-up to Day 60:

- Time to all-cause mortality
- Time to first discharge from investigator site
- Time to first discharge to non-hospitalized residence

The following exploratory endpoints will be analysed using time to event analyses with a follow-up to Day 28:

- Time to recovery from respiratory failure
- Time to last dependence on supplementary oxygen
- Time to final ICU discharge

For time to event endpoints where the event is a worsening participant status, participants with missing data due to study withdrawal prior to occurrence of the event will be censored at the time of study withdrawal, participants alive at the end of follow-up will be censored at the time of end of follow-up (*i.e.* Day 28/60).

For time to event endpoints where the event is an improvement participant status, participants with missing data due to study withdrawal prior to first occurrence of the event will be censored at the time of end of follow-up. The end of follow up will be the earliest of the nominal timepoint (*i.e.* Day 28/60) and their actual study day of visit. If a participant meets the endpoint at the point of withdrawal, then the participant will be assumed to have achieved the event.

The endpoint will be analysed using a Cox proportional hazards model adjusted for covariates per Section 4.1.1. Ties will be broken using Efron's method. The hazard ratio of the treatment group and corresponding confidence interval and p-value will be reported. For any endpoint where a hazard ratio above 1 indicates improvement of otilimab over placebo, the inverse hazard ratio will also be presented. For model checks refer to Section 6.2.3.

Kaplan-Meier plots will be presented by treatment group. Estimates of the median time-to-event and other relevant percentiles will be derived from the unadjusted Kaplan-Meier plots and reported in a table. If 50% of participant do not meet the event definition during the study, alternative percentiles may be produced.

These time to event endpoints may also be derived using additional follow-up times to support future sensitivity analyses.

Additionally, for time to ICU discharge, the following summaries will be produced:

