6.2. Appendix 2: Statistical Modelling

6.2.1. Multiple Imputation

Multiple imputation will be utilized to impute data that is missing following intercurrent events as detailed in the endpoint derivations.

For endpoints that are derived from the clinical status ordinal scale, as shown below, missing data will first be imputed on the ordinal scale prior to deriving the binary endpoints:

- All-cause Mortality
- Alive and Free of Respiratory Failure
- Alive and Independent of Supplementary Oxygen

For other endpoints, missing data will be imputed directly on the binary endpoint.

A monotone logistic regression imputation will be performed on both binary and ordinal endpoints adjusting for treatment and the analyses covariates.

This will be performed in a stepwise fashion, where each visit will be imputed from the selected visits preceding it, such that intermediate missing data (data that is between two non-missing values) will be imputed based only on the data that precedes it.

Death will always be considered a permanent event, such that if a subject is imputed to have died, missing data succeeding it will always be assigned the state of 'died'.

As it is expected that the data may have either a complete separation pattern or a quasi-complete separation pattern, observations will be added to each response group and then this augmented data will be used to fit a weighted logistic regression as proposed by [White \(2010\)](#)

If the logistic regression step fails to converge despite augmenting the likelihood, then a discriminant function [[Brand, 1999](#)] may be used in place of the logistic function.

A sufficient number of imputations will be performed to ensure the stability of the estimates, 10,000 imputation will be used. The results of analysis from each complete imputed dataset will be combined using Rubin's rule. [Table 4](#) details the models, covariates and the seed to be used for the analyses.

For subgroup analyses the multiple imputation model will be identical to the main endpoint analyses and the interaction term will be added into the analysis step. The chi-squared test statistic of the interaction term will be pooled using the procedure of [Rubin \(1987\)](#) and [Li \(1991\)](#).

Table 4 Multiple Imputation Specifications

Endpoint	Covariates	Post-Baseline Timepoints Included in Prediction Model	Initial Seed

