Participants alive and free of respiratory failure at Day 7, 14, 28, 42, and 60. All-cause mortality at Day 28, 60. Participants alive and independent of supplementary oxygen at Day 7, 14, 28, 42, and 60	See Section 4.1.6.1	Days 7,14,28,42 and 60	122
If the number of participants is small within a category of a covariate, then the covariate categories may be refined. If the category cannot be refined further, then the covariate may be included as a continuous measure.			

The seeds were generated using the following code:

```
DATA seeds;
DO i=1 to 1;
  seed=int(10000*ranuni(21409402));
  OUTPUT;
END;
RUN;
```

If additional seeds are required, then the initial seed as specified will be incremented by one.

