6.3. Appendix 3: Selected Considerations for Data Analyses and Data Handling

6.3.1. Assessment Windows

All data, except efficacy data, laboratory assessments, and vital signs assessments will be reported according to the nominal time of clinic visits and assessments as specified in the protocol. Laboratory and vital signs assessments will be analyzed based on the visit information recorded in the eCRF. Data for unscheduled visits will be assigned to a scheduled visit if the visit date falls within the corresponding visit window as specified below. For statistical analysis it is important to keep the intermediate data, so for efficacy data, visit slotting will be conducted in addition to the actual timepoint. Lab, vital signs, and efficacy data will be slotted according to the windows specified below. Where data is collected daily, this will be analyzed based on the data recorded in the eCRF.

In case of multiple assessments slotting to the same visit, nominal visit will take precedence. If two assessments slot to the same visit and does not include the nominal visit, then the one closest to the nominal visit will take precedence with the last assessment taking precedence if they are equidistant from the nominal visit.

Analysis Set / Domain	Parameter (if applicable)	Target	Analysis Window		Analysis Timepoint
			Beginning Timepoint	Ending Timepoint	
LAB	All	Day 4	Day 3	Day 5	4
		Day 7	Day 6	Day 8	7
		Day 14	Day 13	Day 15	14
		Day 28	Day 27	Day 29	28
Vital Signs	Blood pressure, pulse, respiratory rate and temperature	Day 4	Day 3	Day 5	4
		Day 7	Day 6	Day 8	7
		Day 14	Day 13	Day 15	14
		Day 28	Day 27	Day 29	28
Efficacy	Ventilation Status, Clinical Status, signs and symptoms of COVID-19	Day 4	Day 3	Day 5	4
		Day 7	Day 6	Day 8	7
		Day 14	Day 12	Day 16	14
		Day 28	Day 26	Day 30	28
		Day 42	Day 40	Day 44	42
		Day 60	Day 53	Day 67	60

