6.3.2.2. Clinical Status Ordinal Scale

Additional derivation of clinical status will be performed. If subject dies then their clinical status will be recorded as 8-Death from date of death to Day 60 inclusive, this will override any collected clinical status.

Otherwise if clinical status is missing and the assessment day is prior to last contact with participant, then the following rules will apply:

Category	Rule
8 - DEATH	Date of death <= date of assessment
7 - HOSPITALIZED, MECHANICAL VENTILATION+ADDITIONAL ORGAN SUPPORT	Ventilation = "INVASIVE MECHANICAL VENTILATION" and additional support includes: "EXTRACORPOREAL MEMBRANE OXYGENATION" "RENAL REPLACEMENT THERAPY (RRT)/DIALYSIS" "INOTROPES/VASOPRESSORS"
6 - HOSPITALIZED, INTUBATION AND MECHANICAL VENTILATION	Ventilation = "INVASIVE MECHANICAL VENTILATION" and does not meet the classification for additional organ support

Category	Rule
5 - HOSPITALIZED, HIGH-FLOW OXYGEN(\geq 15L/MIN), CPAP, BIPAP, NIV	Ventilation is: "NON-INVASIVE MECHANICAL VENTILATION" or "HIGH-FLOW OXYGEN THERAPY (\geq 15 L/MIN)"
4 - HOSPITALIZED, LOW-FLOW OXYGEN BY MASK OR NASAL PRONGS	Ventilation = "LOW-FLOW OXYGEN THERAPY" and date of discharge to non-hospitalized residence is missing or greater than date of assessment
3 - HOSPITALIZED, NO OXYGEN THERAPY	Date of assessment < date of discharge to non-hospitalized residence and Date of assessment > date of last oxygen usage
2 - NON-HOSPITALIZED, LIMITATION OF ACTIVITY	Date of assessment > date of discharge to non-hospitalized residence and participant has not been re-hospitalized and date of assessment > date of last oxygen usage and does not meet the classification for group 1.
1 - NON-HOSPITALIZED, NO LIMITATION OF ACTIVITY	Date of assessment > date of discharge to non-hospitalized residence and participant has not been re-hospitalized and date of assessment > date of last oxygen usage and last and subsequent recorded assessment is "1 - NON-HOSPITALIZED, NO LIMITATION OF ACTIVITY".

All non-Death derived values will be flagged in the dataset.

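### Part 2 imputation can record death at Day 28 for a participant later seen alive, and it ignores a recorded discharge on about Days 17-25; both effects are small and cheap to remove

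*SAP*

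**What the plan says.** All SAP references are to the Part 2 plan.

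- **Imputation (SAP 6.2.1, Table 4).** Status is imputed on the ordinal scale before the binary endpoints, including all-cause mortality, are derived. Imputation is stepwise: "each visit will be imputed from the selected visits preceding it". Table 4 lists the post-baseline timepoints as "Days 7,14,28,42 and 60" and takes its covariates from 4.1.6.1 (treatment, baseline clinical status, sex, age). A gap between two observed visits is filled from earlier data only. An imputed death carries forward to later missing visits; nothing is said about later observed ones.
- **Windows (SAP 6.3.1).** "Lab, vital signs, and efficacy data will be slotted according to the windows specified below". For efficacy, Day 14 covers Days 12-16 and Day 28 covers Days 26-30.
- **Derivation (SAP 6.3.2.2).** Status is rebuilt from ventilation and discharge data "if clinical status is missing and the assessment day is prior to last contact with participant". Section 4.2.1 puts the limit at study withdrawal instead, while referring to 6.3.2.
- **Follow-up.** Protocol 1.4, footnote 6: "If the participant is discharged between Day 15 and Day 27, the Day 28 visit will be replaced with a phone call". Protocol 8.4.2 expects little missing data, of which "most will be lost to follow up data after discharge". Under Protocol 6.8, if a participant remains unreachable, "he/she will be considered to have withdrawn from the study".
- **Time to event (SAP 4.3.2.2).** For endpoints that mark improvement: "If a participant meets the endpoint at the point of withdrawal, then the participant will be assumed to have achieved the event".

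**The concern.** Two features look wrong.

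1. Forward-only imputation does not use the fact that a participant was later seen alive. If Day 28 is left missing, category 8 is a possible draw, and the death rule does not remove it. The record can then read dead at Day 28 and alive at Day 42. This touches the primary endpoint and Day 28 mortality, which is second in the testing hierarchy (SAP 2.1).
2. The group the protocol expects to be missing most is imputed without the most informative fact recorded about it, namely discharge. The plan credits that same fact in time to recovery from respiratory failure, fourth in the hierarchy. Missing at random is then less plausible than the available data would allow.

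**Working it through.** **Plan's own figure.** With 45% versus 60%, two-sided 5% (the same critical value as one-sided 2.5%), the usual two-proportion formula gives 173 per arm, 346 in total, with power 80.0%. The smallest significant difference is about 10.55 points, against the stated 10.6%. The standard error of the difference is sqrt(0.45×0.55/173 + 0.60×0.40/173) = 5.31 points.

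**Part 1: impossible deaths.** Take a participant at home on low-flow oxygen who misses Day 28 but is reached at Day 42. Day 28 precedes last contact, so 6.3.2.2 applies:

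- Category 4 needs the discharge-home date to be missing or later than the assessment: fails.
- Category 3 needs the assessment to precede discharge home: fails.
- Categories 1 and 2 need oxygen to have ended: fail.

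No category results, so Day 28 goes to imputation. A participant off oxygen in hospital with no discharge-home date is similar when the rules are read literally: category 4 provides for a missing date and category 3 does not. Protocol 7.2.7 records discharge to a hospitalized facility, so this case can arise.

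Size, home oxygen only. Assume 50% of an arm is home by Day 28, 10-30% of those are on oxygen, and 2-5% of those miss Day 28 but are reached later:

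- 173 × 0.5 × 0.10 × 0.02 = 0.17
- 173 × 0.5 × 0.30 × 0.05 = 1.30

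These are underived statuses per arm. Impossible deaths are this count times the chance of drawing category 8, so fewer. The hospital case is not quantified.

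**Part 2: discharge not used.** Days 17-25 fall in neither efficacy window. If last contact is about the discharge date, 6.3.2.2 does not reach Day 28. Day 28 is then imputed from treatment, baseline status, sex, age and Day 7 and Day 14 status.

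Bias in the difference = -(s_t·l_t·g_t - s_c·l_c·g_c), where t is otilimab and c is placebo. Here s is the share discharged on Days 17-25, l the share of those lost, and g the true minus imputed Day 28 response. The documents give none of these, so two illustrative daily multistate models were calibrated to 45% versus 60%:

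- *Model A*: s = 13-21%. If true response after such a discharge is 99%, 95% or 91%, the plan imputes 67-88%, 67-86% or 67-84%.
- *Model B*: s = 12.1% (placebo) and 14.0% (otilimab). True response is about 99.6% and the plan imputes about 59-66%.

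Example, Model B, 5% placebo versus 10% otilimab loss: 0.1402 × 0.10 × (0.996 - 0.650) = 0.485 points; 0.1209 × 0.05 × (0.998 - 0.609) = 0.235 points. The bias is -0.25 points.

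| Loss, placebo / otilimab | Model A, points | Model B, points |
|---|---|---|
| Equal, 2-10% | at most 0.02 | at most 0.01 |
| Equal, 30% | not run | 0.06 |
| 5% / 10% | 0.05-0.25 | 0.25 |
| 5% / 15% | 0.11-0.50 | 0.49 (by the formula, same gaps) |
| 10% / 30% | not run | 1.07 |
| 0% / 30% | not run | 1.54 |

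The arm that loses more discharged participants is penalised. The largest 5% / 15% figure is 0.50/5.31 = 0.09 standard errors. At 5% loss, 173 × 0.13 × 0.05 = 1.1 to 173 × 0.21 × 0.05 = 1.8 participants per arm are affected. A deliberately extreme corner of the formula (s_t = 26%, loss 0% / 30%, g = 0.6) gives 0.26 × 0.30 × 0.6 = 4.7 points; nothing in the documents points there.

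**The case against.** The strongest reply is that little turns on this. The tipping-point analysis (SAP 4.2.3.1) varies the response of missing participants from 0 to 1 independently by arm, and 4.3.3.1 extends it to the ranked binary endpoints. With equal loss, a discharge predictor gains nothing: its largest bias in Model A is 0.04 points, against 0.02 for the plan. The direction is also uncertain. The plan under-imputes only if true response among lost participants exceeds about 67-88% (Model A) or 59-66% (Model B). In patients aged 70 or over, loss could reflect readmission or death. All of this stands, and it keeps the priority low. It does not remove an impossible record, and the tipping-point analysis does not change the primary estimate.

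Three further replies stand in part. Section 4.1.6.1 allows additional covariates, and the OPS may hold further data-handling rules; the SAP does not state either for this case. The ordinal-scale table is redacted, so a note on home oxygen could exist there; the derivation rules in 6.3.2.2 are visible and have none. Different endpoints may legitimately have different missing-data rules, so the contrast with 4.3.2.2 is not an error in itself. It does show that the plan regards discharge as informative.

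A reader might infer more than the documents support:

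- *That the primary comparison is materially biased.* This needs loss that is both high and unequal, and no loss rate is given.
- *That Day 28 is certain to be imputed.* If study withdrawal (4.2.1) governs and is dated after the failed contact attempts, Day 28 might be derived.
- *That every Day 15-27 discharge depends on one call.* Inpatient status on Days 26-27 already lies in the Day 28 window, so this holds only for Days 15-25.
- *That 0.2-1.3 per arm counts false deaths.* It counts underived statuses.

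**Conclusion.** Both gaps are real on the text, and both are minor.

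The first is a rule that can produce a logically impossible record. It is rare, and its frequency rests on assumed rates of home oxygen and missed calls.

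The second holds if last contact governs and the participant was free of respiratory failure at discharge. A transfer while still in category 5 or above would not count as recovered. Bias in the treatment difference is negligible with equal loss and about 0.05-0.5 points, under 0.1 standard error, with 5% versus 10-15% loss. The imputed response is model-dependent (59-88% across the two models), but both lead to the same conclusion. The sign reverses if lost participants do badly enough. Neither gap gives grounds to doubt the planned primary conclusion.

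**What to change.** Low priority, in the SAP:

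1. In 6.2.1, do not allow category 8 to be imputed at a visit before a date on which the participant is known to be alive.
2. In 6.3.2.2, assign categories for low-flow oxygen after discharge home and for participants off oxygen in hospital with no discharge-home date. If the OPS already does this, cite it.
3. Align 4.2.1 with 6.3.2.2 on whether study withdrawal or last contact ends derivation.
4. In Table 4, add one predictor defined for everyone: discharged to a non-hospitalized residence before Day 26, or last recorded status before the Day 28 window.

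Keep the stepwise method and the tipping-point analysis. The cost is wording and minor programming on data already collected. Sparse cells are possible, but the augmented regression in 6.2.1 already addresses separation. The new predictor over-imputes somewhat in Model A (0.4-5.4 points among those lost) and is optimistic if lost participants do worse than followed ones; the tipping-point analysis covers that.

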4.1.5. Missing Data Handling Rules

Unless otherwise stated the following rules will be applied to all Primary and Secondary endpoints:

- Missing data can occur due to study withdrawal or participants lost to follow-up before the completion of the study or due to intermittent missing values (*i.e.* data between two non-missing assessments).
- Missing data will be imputed under a missing at random (MAR) assumption using a multiple imputation (MI) model, unless otherwise specified. The MI model will include covariates; treatment, clinical status at baseline, sex and age group and baseline of the variable of interest (if appropriate). More details will be provided in [Appendix 2](#).

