4.3.1. Endpoint Definition

4.3.1.1. All-cause Mortality at Day 28 and 60

Participants will meet the endpoint if they have died due to any cause prior to Day 28 and 60. All-cause mortality will be based on the clinical status as defined in Section 6.3.2.

4.3.1.2. Time to All-cause Mortality up to Day 60

Defined as the time (days) from dosing to death, due to any cause, up to (and including) Day 60.

4.3.1.3. Participants Alive and Free of Respiratory Failure at Day 7, 14, 42, and 60

Defined as per primary endpoint, see Section 4.2.1.

4.3.1.4. Time to Recovery from Respiratory Failure up to Day 28

Defined as the time (days) from dosing to last recovery from respiratory failure up to (and including) Day 28. Participants are in respiratory failure if they are in category 5 or above from the GlaxoSmithKline (GSK) modified ordinal scale adapted from World Health Organization (WHO, 2020) scale 2020 (Table 2).

Note: if a participant has recovered from respiratory failure but then progresses back into respiratory failure on or prior to the end of follow up (Day 28) the participant has not had their last recovery from respiratory failure.

This endpoint will use a composite approach for death such that if the intercurrent event of death occurs (on or prior to Day 28), then time will be censored at end of follow up (Day 28).

4.3.1.5. Participants Alive and Independent of Supplementary Oxygen at Day 7, 14, 28, 42, and 60

Participants are independent of supplementary oxygen if they are in category 1, 2 or 3 from the GlaxoSmithKline (GSK) modified ordinal scale adapted from World Health Organization (WHO, 2020) scale 2020 (See Table 2- Ordinal Scale). Missing data prior to study withdrawal will be derived using ventilation data as described in Section 6.3.2

Participants will meet the endpoints if they are alive and independent of supplementary oxygen at Day 7, 14, 28, 42, and 60 respectively. As participants may be discharged from investigator site, analysis windows will be used to define the endpoint as described in Section 6.3.1.

4.3.1.6. Time to Last Dependence on Supplementary Oxygen up to Day 28

Defined as the time (days) from dosing to last dependence on supplementary oxygen up to (and including) Day 28. Participants are dependent on supplementary oxygen if they are in category 4 or above from the GlaxoSmithKline (GSK) modified ordinal scale adapted from World Health Organization (WHO, 2020) scale 2020 (Table 2).

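### Part 2 SAP 6.2.1 can impute death at Day 28 for a participant later observed alive, and the 6.3.2.2 derivation that closes most such gaps leaves some living states without a category

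*SAP*

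**What the plan says.** **Imputation (Part 2 SAP 6.2.1).** Mortality, freedom from respiratory failure and independence from oxygen are all derived from the ordinal clinical status, which is imputed first. The model uses Days 7, 14, 28, 42 and 60, with 10,000 imputations. It works forward, visit by visit, "such that intermediate missing data (data that is between two non-missing values) will be imputed based only on the data that precedes it". The only operative rule on death is that "if a subject is imputed to have died, missing data succeeding it will always be assigned the state of" death.

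**Scope (4.1.5).** Intermittent missing values are named as a source of missing data. The general rule is: "Missing data will be imputed under a missing at random (MAR) assumption using a multiple imputation (MI) model, unless otherwise specified".

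**Derivation before imputation (4.2.1 and 6.3.2.2).** Section 4.2.1 says that status missing before study withdrawal is derived from ventilation data under 6.3.2. The rules in 6.3.2.2 apply "Otherwise if clinical status is missing and the assessment day is prior to last contact with participant". The relevant conditions are:

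- Category 4 (hospitalized, low-flow oxygen): "date of discharge to non-hospitalized residence is missing or greater than date of assessment".
- Category 3 (hospitalized, no oxygen): "Date of assessment < date of discharge to non-hospitalized residence", and the assessment falls after last oxygen use.
- Categories 1 and 2 (not hospitalized): the assessment falls after home discharge and after last oxygen use, and the participant has not been re-hospitalized.

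**Endpoints that depend on it.** The primary endpoint uses this status. Section 4.3.1.1 adds: "All-cause mortality will be based on the clinical status as defined in Section 6.3.2". Day 28 and Day 60 mortality are steps 2 and 3 of the hierarchy in 2.1.

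**The concern.** Permanence of death has two consequences. Someone dead at one visit is dead at every later visit, and someone alive at a visit was alive at every earlier one. Section 6.2.1 states the principle but applies only the first consequence, and only to visits that are missing. Because the model conditions on earlier visits alone, a later observation of life does not enter it. If Day 28 and Day 42 are both missing and Day 60 is observed alive, an imputed Day 28 death is even carried to Day 42 before Day 60 contradicts it.

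In such an imputed dataset one person counts as a death in Day 28 mortality and a non-responder on the primary endpoint, yet as alive in Day 60 mortality. The observed data exclude that result. The practical question is whether such a gap can still reach the imputation once 6.3.2.2 has been applied.

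**Working it through.** **1. The plan's own figure, for context.** No stated figure is disputed. With 45% versus 60%, one-sided 2.5% and 80% power, the mean proportion is 0.525 and n per arm = [1.960 × √(2 × 0.525 × 0.475) + 0.842 × √(0.45 × 0.55 + 0.60 × 0.40)]² / 0.15² = 172.8, so 173 per arm and 346 in total (SAP section 5). This is unaffected.

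**2. Which gaps survive the derivation.** Take a living participant with no Day 28 status and a later contact, so that the 6.3.2.2 trigger is met. Reading the rules literally:

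| State at Day 28 | Result |
|---|---|
| High-flow oxygen, non-invasive or invasive ventilation | Category 5 to 7; these rules carry no discharge condition |
| At home, off oxygen for good, not re-hospitalized | Category 1 or 2 |
| Off oxygen in a facility, home later with no further oxygen | Category 3 |
| Low-flow oxygen at home | None: category 4 fails on the discharge date, 1 and 2 on last oxygen use |
| Off oxygen, no home-discharge date ever recorded | None if read literally: category 3 lacks the missing-date clause that category 4 has |
| Re-hospitalized after going home, on no or low-flow oxygen | None if the first discharge date is meant; 3 or 4 possible if a later one is used |

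Coding the rules over 5 locations × 8 oxygen or ventilation states gives 40 combinations. Of these, 15 receive no category, or 16 if a missing discharge date fails the category 3 inequality. Beyond the states above, the unmatched ones are edge cases: assessment on the day of discharge, ventilation coded Other, and off oxygen now but on it again later.

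Home oxygen is plainly foreseen. Protocol 1.4 and 7.2.4 collect it after discharge, and SAP 4.4.1.10 tabulates it. Discharge to a hospitalized facility is a recorded location (protocol 7.2.7), and 6.3.2.2 itself mentions re-hospitalization.

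**3. How narrow the route is.** Under 6.3.1, "for efficacy data, visit slotting will be conducted in addition to the actual timepoint", and the Day 28 window is Day 26 to 30. Status is recorded daily until discharge or Day 28. The participant will therefore usually have left the site before Day 26, have no status in the window, be in an unmatched state, and be contacted alive later.

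**4. Size (all rates and counts assumed; the documents give none).** An illustrative simulation used 346 participants, 60 replicates and two assumed Day 14 to Day 28 transition tables (Day 28 mortality 34% and 29%). A cumulative-logit model was fitted on Day 14 status, treatment, baseline category, sex and age. The fitted probability p of category 8 for a known survivor was:

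- Day 14 category 4: 3.6% to 6.6%
- Day 14 category 5 (Day 28 truly category 4): 17.8% to 23.6%

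For k affected survivors in one arm, expected deaths = k × p, and the shift in that arm = 100 × k × p / 173 points.

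- k = 1: 0.04–0.07 or 0.18–0.24 deaths; 0.02–0.04 or 0.10–0.14 points. That person is dead at Day 28 in 10,000 × p = 360–660 or 1,780–2,360 datasets.
- k = 3: 0.11–0.20 or 0.53–0.71 deaths; 0.06–0.11 or 0.31–0.41 points.

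The standard error of the mortality difference is √(2m(1−m)/173) = 4.9 points at m = 29% and 5.1 at m = 34%, so 0.41/5.1 = 0.08. Three gaps split 2:1 net to the k = 1 shift, and equal numbers in the two arms net to about zero.

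**5. A wider bracket.** With 2 to 10 gaps in an arm and p from 1% to 20%, expected deaths run from 0.02 to 2.0 (0.01 to 1.16 points). A tenth of a standard error is 0.49 points. At p = 23.6% one gap is worth 0.136 points, so reaching it takes 0.49/0.136 = 3.6, that is four gaps in one arm and none in the other. At 6.6% (0.038 points each) it takes 13.

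**The case against.** The strongest reply is that the SAP already keeps these participants out of the imputation. Section 4.2.1 has status before withdrawal derived, 4.3.1.5 repeats this for the oxygen endpoint, and 4.3.1.1 bases mortality on the derived status. Section 4.1.5 yields where something else is specified, and 6.2.1 opens by limiting itself to data missing after intercurrent events. Someone contacted at Day 42 has not withdrawn by Day 28.

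Much of this stands. A reader might infer from 6.2.1 alone that every intermittent gap is imputed; the documents do not support that, since the derivation clearly comes first and closes most gaps. What remains open is the unmatched state. No text says what happens to it, and 6.2.1 expressly describes imputing values that lie between two observed ones.

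Other limits also stand:

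- The ordinal scale table is redacted, so the scale itself may place home oxygen; the visible derivation rules do not.
- Data-handling detail is deferred to the Output and Programming Specification, which was not available and could contain a check.
- The Day 28 call has a ±2-day allowance that matches the analysis window, and protocol section 7 stresses making it on the day.
- The probabilities above come from a Day 14-only model with assumed transitions. The SAP's model can use other preceding visits and augmented logistic regression. The figures indicate scale only.
- The planned tipping-point analyses cover Day 28 response and both mortality endpoints, and vary the rate among missing participants from 0 to 1. They would show whether these cases matter, but they leave the main estimate unchanged.

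A reader might also infer that Day 28 mortality is materially biased or that power is at risk. Nothing in the documents supports a large or one-sided number of such gaps.

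**Conclusion.** The inconsistency is real on the text. Section 6.2.1 permits category 8 before a visit at which the participant was observed alive, and no other Part 2 section forbids it. The 6.3.2.2 rules leave at least one foreseen state, low-flow oxygen at home, through which a known survivor can reach the imputation. The other two states depend on how a missing discharge date, or a second discharge, is read.

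Severity is low. For a handful of gaps the effect on Day 28 mortality is likely well under 0.1 standard error: 0.14/4.9 = 0.03 for one participant at the highest simulated probability, and 0.08 for three in one arm. The primary response shifts by the same number of points if the person was truly a responder. This rests on the number of gaps being very small, which is a judgement the documents neither confirm nor contradict. The reason to act is that a confirmatory analysis should not contain outcomes its own data rule out.

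**What to change.** 1. In 6.2.1, do not allow category 8 at any visit on or before the last date the participant is known to be alive. These false deaths are then zero by construction.
2. In 6.3.2.2, add the missing-date alternative to the category 3 discharge condition, as category 4 already has it. Assign low-flow oxygen at home, and re-hospitalization on no or low-flow oxygen, to whichever category the ordinal scale gives them, so that known status is derived and not imputed.

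Reporting the number of remaining intermittent gaps by arm would let readers confirm that the effect is negligible. The cost is SAP wording and programming before unblinding. No new data or participants are needed, and the sample size is unchanged.
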